Participants are instructed not to smoke or ingest any nicotine from waking up until session start at ~9 am, verified by expired CO \leq 7 ppm. If this threshold is exceeded, the session may be rescheduled. Participants first complete the MTWS, AWS, & QSU (see above). The nicotine discrimination procedure is then started. Participants are informed that their task is to compare different types of cigarettes, and that nicotine content is one of the parameters in which these cigarettes may differ. On each trial, participants take four 2-s puffs via the Clinical Research Support System (CReSS) portable device, to standardize smoking topography, with 30 s between puffs (71-74). Puff duration and inter-puff interval is timed by visual cues on an instruction screen. The CReSS time-stamps puff onset and duration. Trials are separated by 20 min no smoking.

The first 2 trials are reference trials, over which participants take 4 puffs on the Very Low Nicotine Content (VLNC) and the 0.8 mg-yield cigarette each, with sequence counterbalanced across participants. The two cigarettes are identified by letter code (A and B, counterbalanced). Four discrimination trials follow, in which the participant is blind with regards to cigarette identity. The sequence in which the two cigarette types are sampled (ABBA, BAAB, ABAB, BABA) is counterbalanced and double-blind, i.e., only the statistician and dispensing pharmacist know the sequence. After each discrimination trial, participants choose whether the sampled cigarette was of type A or B, complete the MTWS, AWS, QSU, and mCEQ, and indicate on a scale from 1 to 5 how much they want to smoke a cigarette like this, and how satisfying and how strong they thought the cigarette was. After the 4th discrimination trial, participants have a break and a light lunch, staying on the premises to ensure continued smoking abstinence. They then receive another reference trial with the VLNC and 0.8-mg cigarette each, and complete another 4 discrimination trials as described above.

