Some participants may already have done a SCID in the context of clinical care or another study. If this SCID was done at the MPRC, it will not be redone. The diagnostic information will have entered clinical records and will be accessed under a partial HIPAA privacy waiver.

3 * Describe the duration of an individual participant's participation in the study:

The shortest time within which the study can be completed by any participant is 1 week. A maximum of 3 months may expire between any of the four sessions described above (although efforts will be made to not exceed 2 weeks). Thus, the maximum completion time is 9 months.

4 * Describe the amount of time it will take to complete the entire study:

The is a two-year study.

5 * Describe any additional participant requirements:

None.

ID: VIEW4E0280585B400
Name: v2_Study Procedures

Sample Size and Data Analysis

If you uploaded a separate research protocol document in the 'Research Protocol' page, cite the applicable section and page numbers from that document in the answer boxes below.

1 * Provide the rationale and sample size calculations for the proposed target population:

Power analyses indicate that, at $\beta=0.8$, $N=45$ per diagnostic group would enable detection of medium effect sizes (Cohen's $d=0.6$, Cohen's $f=0.3$) with the analyses described below. To prepare for a 20% attrition rate, we will randomize 112 participants for 90 completers. Based on an expected 20% screening failures, we anticipate that screening 140 volunteers will result in 112 enrollments, but to be on the safe side, we set the enrollment ceiling at 160.

2 * Provide the plan for data analysis. Include in the description the types of comparisons that are planned (e.g., comparison of means, comparison of proportions, regressions, analysis of variance, etc.), which is the primary comparison/analysis, and how the analyses proposed will relate to the primary purposes of the study:

- Hypothesis 1 (smoking is under greater cue control in SmoSz than SmoCon) is tested by two-sample t-test comparing groups on breath CO after 8 hrs of ad libitum VLNCcig smoking (ANCOVA if group matching is suboptimal for 1 or more variables). Secondary analysis: ANOVA (or ANCOVA) to compare groups on the number of VLNCcigs smoked in the first vs. last 2 hrs of the Ad Lib Smoking Session (group x time point).

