- Hypothesis 2 (SmoSz are less sensitive to subjective nicotine effects than SmoCon) is tested by two-sample t-test (or ANCOVA) comparing nicotine discrimination accuracy between groups. Secondary analysis: The composite subjective state score after smoking a VLNC or a 0.8 mg-yield cigarette is compared between SmoSz and SmoCon by ANOVA (group x cigarette type), or ANCOVA if indicated (see above).

- Hypothesis 3 (nicotine sensitivity is related to cue control and can account for the group difference therein): Regression analysis tests the impact of discrimination accuracy on cue control while controlling for the group effect. To evaluate the degree to which nicotine insensitivity can statistically account for the group difference in cue-control, we measure the reduction in the group effect when entering discrimination accuracy, with a >25% reduction in β group defined as significant. To determine the percentage of between-group variance in cue control statistically accounted for by nicotine sensitivity, we quantify the reduction in variance explained by the group factor when including discrimination accuracy as a covariate in ANCOVA.

- Hypothesis 4 (cognitive control deficits can account for cue-control and for the group difference therein) is tested in a manner analogous to Hypothesis 3.

ID: VIEW4E02806052800
Name: v2_Sample Size and Data Analysis

Sharing of Results

1 * Describe whether results (study results or individual subject results, such as results of investigational diagnostic tests, genetic tests, or incidental findings) will be shared with subjects or others (e.g., the subject's primary care physicians) and if so, describe how it will be shared:

If significant abnormalities are identified during screening, these test results would be given to the subject, together with a recommendation regarding the appropriate type of follow-up (e.g., see family doctor or specialist). With written authorization from the participant, test results may also be shared with their care provider.

The overall trial outcome would not be shared with individual participants or their providers but will be made accessible via scientific publication.

ID: VIEW4E02808CBD800
Name: v2_Sharing of Results

Research with Drugs or Biologics

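### The plan does not say that cigarette order, letter code and test sequence are balanced within each diagnostic group, and the H2 test has no order term: a minor, nearly free improvement

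*Combined protocol and SAP*

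**What the plan says.** Study Procedures, item 1, Nicotine Discrimination Session, sets three order features for each participant.

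- **Reference order** (very low nicotine or 0.8 mg cigarette first): "with sequence counterbalanced across participants".
- **Letter code**: "The two cigarettes are identified by letter code (A and B, counterbalanced". The parenthesis gives no further detail.
- **Test sequence**: "The sequence in which the two cigarette types are sampled (ABBA, BAAB, ABAB, BABA) is counterbalanced and double-blind". The statistician and the dispensing pharmacist hold it.

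The words about participants attach to the reference order alone. For the other two features no unit of balance is given. How the list is built is not described, nor whether the second block of four trials repeats the first block's sequence.

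Under Sample Size and Data Analysis, item 2, H2 "is tested by two-sample t-test (or ANCOVA) comparing nicotine discrimination accuracy between groups". The condition for covariate adjustment stands under Hypothesis 1: "ANCOVA if group matching is suboptimal for 1 or more variables". Neither place names order, code or sequence. The same accuracy score is a regressor in Hypothesis 3.

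**The concern.** Diagnosis cannot be allocated. In this session the order features are the only thing the trial assigns between participants. Balance over the whole sample does not ensure balance in each group, and H2 compares the groups.

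Code and sequence together decide whether a morning-abstinent smoker's first test cigarette is the 0.8 mg or the very low nicotine one. Sequence also decides whether the types alternate or mirror. These differences lie between participants, so a participant's own trials do not cancel them. If they affect accuracy and fall unevenly across the groups, part of the observed H2 difference reflects order. If they fall evenly but are left out of the model, they still inflate the residual variance. At stake is some precision in the H2 contrast and some noise in the score passed on to Hypothesis 3.

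**Working it through.** **The plan's own figure.** Inputs from Sample Size and Data Analysis, item 1: d = 0.6, 80% power, 45 per group. Alpha is not stated; 0.05 two-sided is assumed. The exact t-test needs 44.6 per group, so 45, with power 0.804. The plan's figure reproduces. Attrition: 90/0.8 = 112.5, against 112 in the plan, or 56 entered per group if the groups are equal.

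**Imbalance under one overall list unrelated to diagnosis.** Take a two-level order feature with 45 of the 90 completers at each level. The number k in one group with the first order is hypergeometric (90, 45, 45).

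- SD(k) = sqrt(45 × 0.5 × 0.5 × 45/89) = 2.385.
- The difference in shares is (2k − 45)/45, with SD 2 × 2.385/45 = 0.106, mean 0 and a 95% range of about ±0.20.

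**Shift in the H2 contrast.** Shift = order effect × difference in shares. The documents give no order effect, so 0.2, 0.5 and 0.8 SD are assumed. At the 95th percentile the shift is 0.20 × 0.2 = 0.04, 0.20 × 0.5 = 0.10 and 0.20 × 0.8 = 0.16 SD. The standard error of the contrast is sqrt(2/45) = 0.21 SD.

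**Simulation.** 112 entered, 45 completers per group, two-level order, 20,000 runs per setting, true d = 0.6 in units of the SD within an order. All entries below are for the t-test without an order term.

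| Order effect (SD) | 95th percentile shift, one list | Same, one list per group | Type I error, one list | Power, one list | Power, one list per group |
|---|---|---|---|---|---|
| 0.2 | 0.04 | 0.02 | 0.051 | 0.800 | 0.802 |
| 0.5 | 0.10 | 0.04 | 0.049 | 0.783 | 0.788 |
| 0.8 | 0.16 | 0.07 | 0.048 | 0.742 | 0.749 |

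**Why type I error holds and power falls.** An order effect e split half and half adds e²/4 to the variance. At e = 0.8 that is 0.16, so the SD becomes sqrt(1.16) = 1.077 and the effective d becomes 0.6/1.077 = 0.557. The t-test's own variance estimate already contains this term, so chance imbalance is covered by the standard error. Per-group lists alone reduce the true variability of the contrast but not the estimated variance. The t-test is then slightly conservative: type I error is 0.040 at e = 0.8.

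**Adding the order term.** With the term in the model, power returns from about 0.78 to 0.80 (e = 0.5) and from about 0.75 to 0.80 (e = 0.8), with type I error near 0.05. With no order effect there is no detectable loss. If d = 0.6 is meant in units of the total SD, the t-test already has its 0.80 and the term raises power above it.

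**Feasibility of the list.** Fully crossed there are 2 × 2 × 4 = 16 cells, and 56/16 = 3.5, so exact balance over all three is impossible. Over the test sequence alone, 56/4 = 14; over sequence and code, 56/8 = 7.

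**The case against.** The strongest answer is that the plan is silent rather than wrong. Counterbalancing across participants is ordinary wording for a between-subject order factor and is compatible with balance inside each group. The Study Manual promised in the resources section is a natural place for list construction. The design also limits order effects: every listed sequence contains each cigarette type twice, the reference trials are repeated after lunch, and there are eight discrimination trials in all. A plain tendency to answer with one letter therefore favours no sequence. Finally, the order effects are assumed, and an effect of 0.8 SD is large.

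Most of this stands. It limits the point to an unstated detail and an absent model term. It does not supply either one.

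Three stronger readings are tempting and are not supported.

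- **That the plan balances only over the total sample.** It does not say so, and its words about participants cover the reference order alone.
- **That H2 is biased.** With a list unrelated to diagnosis the expected shift is zero and type I error is 0.048 to 0.051. Serious bias needs a fixed alternating list combined with strictly alternating enrolment of cases and controls. Order would then be fully confounded with group, and type I error would be 0.15, 0.64 and 0.96 for effects of 0.2, 0.5 and 0.8 SD. The documents describe neither condition. Flexible scheduling, separate recruitment sources, screen failures and attrition make the combination unlikely.
- **That per-group lists remove the imbalance.** Attrition leaves a 95th percentile shift of 0.02 to 0.07 SD, and the 16 cells do not divide 56.

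**Conclusion.** The point holds as a minor one. The plan does not state that reference order, letter code and test sequence are balanced within diagnosis, and it plans no order term for H2. Under one overall list the consequence is noise: a 95th percentile shift of 0.04 to 0.16 SD against a target of 0.6 SD, and a power loss from about 0.80 to between 0.80 and 0.74.

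These sizes rest on 45 completers per group, a two-level order feature, attrition unrelated to order, and order effects of 0.2 to 0.8 SD that the documents do not provide. If the true order effect is near zero, almost nothing changes. No error in the plan has been shown.

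**What to change.** - State in the Nicotine Discrimination Session that reference order, letter code and test sequence are balanced within each diagnostic group. The statistician and pharmacist would keep two lists, one per group, approximately balanced over the three features. State also how the second block's sequence is set.
- Pre-specify the counterbalancing factor, at minimum the four-level test sequence, as a term in the primary H2 model whether or not the groups turn out to be matched.

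**Cost.** One extra pharmacy list and a few degrees of freedom: three for the test sequence, taking the error degrees of freedom from 88 to 85, and five if reference order and letter code are added. The sample size, visits and the holders of the blinded sequence do not change. The lists reduce imbalance but do not eliminate it after attrition; the model term adjusts for what remains in the features it includes.

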A factor which may facilitate such stimulus-controlled smoking routines in PSZ is that smokers with schizophrenia (SmoSz) appear remarkably insensitive to subjective effects of nicotine. According to theories of drug dependence, drug effects insensitivity would facilitate a habitual, cue-locked drug taking mode.

Furthermore, automatized drug-taking is reportedly associated with frontoexecutive control deficits, a hallmark of the neurocognitive profile of schizophrenia. Thus, nicotine insensitivity and cognitive control deficits may facilitate automatized, stimulus-driven smoking in SmoSz.

The overall aim of this proposal is to determine whether tobacco smoking in PSZ is under disproportionately strong cue control, and to test whether insensitivity to the subjective effects of nicotine and/or cognitive control deficits can account for this.

Aim 1 is to test whether tobacco smoking behavior is under greater cue control in SmoSz than in matched healthy control smokers (SmoCon). Approach: Indices of cue-controlled smoking are obtained by quantifying the degree to which virtually nicotine-free cigarettes can maintain smoking behavior over eight hours under standardized laboratory conditions, in the presence of transdermal nicotine replacement. Nicotine-free cigarettes evoke a near-complete set of internal and external stimuli and behavioral routines associated with tobacco smoking, but without ensuing nicotine delivery, thus capturing the essence of stimulus control over smoking behavior.

Aim 2 is to test whether SmoSz are less sensitive to the subjective effects of nicotine than SmoCon. Approach: In a standardized laboratory paradigm, SmoSz and SmoCon discriminate research cigarettes of differing nicotine yields, and report on subjective state measures after each cigarette.

Aim 3 is to determine whether nicotine insensitivity is related to cue-control over smoking behavior, and can account for the group difference therein.

Aim 4 is to determine whether cognitive control deficits are related to cue-control over smoking behavior, and can account for the group difference therein. Approach: A cognitive control index will be derived from tasks selected from the RDoC matrix.

2 * Discuss the research design including but not limited to such issues as: probability of group assignment, potential for subject to be randomized to placebo group, use of control subjects, etc.:

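### Discrimination accuracy may partly reflect memory for the A/B code, and no stated model contains both accuracy and the cognitive control index, so the plan cannot separate its two explanations of cue-controlled smoking

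*Combined protocol and SAP*

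**What the plan says.** Study Procedures, item 1, visit 3 (Nicotine Discrimination Session), opens each block with one labelled exposure per cigarette: "The first 2 trials are reference trials". Four blind trials follow. Of the spacing it says "Trials are separated by 20 min no smoking", and of the response "After each discrimination trial, participants choose whether the sampled cigarette was of type A or B". Both references are repeated once, after lunch, before a second block of four. No labelled re-sampling within a block, written reminder of the code, or check that it has been retained is described.

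The overall aim (Justification, Objective, & Research Design, item 1) is to find out whether smoking in schizophrenia is under unusually strong cue control and "to test whether insensitivity to the subjective effects of nicotine and/or cognitive control deficits can account for this".

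In Sample Size and Data Analysis, item 2, Hypothesis 2 compares accuracy between groups by t-test, or by ANCOVA if matching is suboptimal; cognition is not named as a covariate or matching variable. Its secondary analysis compares subjective state by group and cigarette type. For Hypothesis 3, "Regression analysis tests the impact of discrimination accuracy on cue control while controlling for the group effect", with a fall of more than 25% in the group coefficient defined as significant. Hypothesis 4, on cognitive control, "is tested in a manner analogous to Hypothesis 3".

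**The concern.** A correct answer needs three things: a sensed difference between the cigarettes, memory of how each reference felt, and memory of which letter belonged to which. Only the first is nicotine sensitivity. The protocol's own background (items 1 and 3 of the same Justification section) presents cognitive control deficits as a hallmark of schizophrenia, so the groups may also differ on the other two.

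If they do, a lower accuracy in smokers with schizophrenia (SmoSz) can arise at equal nicotine sensitivity, and accuracy in Hypothesis 3 can pick up an effect on cue control that belongs to cognition. Because Hypotheses 3 and 4 are fitted apart, the shared part counts in favour of both. The protocol ties the two answers to different treatment directions (item 4 of that section): discrimination training for one, strengthening of frontoexecutive control for the other. A plan that cannot tell them apart leaves that choice open.

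**Working it through.** **The plan's own figure.** For d = 0.6 at 80% power, assuming two-sided 0.05 (alpha and sidedness are not stated), the t-based calculation gives 44.6, so 45 per group, with power 0.804. This reproduces the plan. The sample size is not in dispute; d = 0.6 serves below as a yardstick.

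**Delay between reference and response.** One trial lasts 4 × 2 s + 3 × 30 s = 98 s, or 1.63 min. In 20-minute steps, references fall at 0 and 20 min and blind trials at 40, 60, 80 and 100 min.
- From the second reference: 20, 40, 60, 80 min.
- From the first reference: 40, 60, 80, 100 min.
- Mean of the eight delays: 480 / 8 = 60 min.

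Adding 1.63 min per trial makes the longest delays 87 and 108 min. The four rating scales after each blind trial take about 4 + 4 + 4 + 5 = 17 min at the stated durations, so the gaps are not idle.

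**Hypothesis 2, illustration.** Assumptions, none from the documents: equal true accuracy p0 of 0.75 to 0.85 in both groups; between-person SD s of 0.08 to 0.12; SmoSz lose the code on a fraction L of trials and then guess; control smokers never lose it. With 8 trials:
- p1 = p0(1 − L) + 0.5L
- SD² = [p0(1 − p0) + p1(1 − p1)] / 2 / 8 + (7/8)s²
- L = 0.20, p0 = 0.75, s = 0.12: p1 = 0.70, SD = 0.1935, d = 0.05 / 0.1935 = 0.26.
- L = 0.20, p0 = 0.85, s = 0.08: p1 = 0.78, SD = 0.1559, d = 0.07 / 0.1559 = 0.45.
- L = 0.30, same two corners: d = 0.075 / 0.1950 = 0.38 and 0.105 / 0.1595 = 0.66.

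A milder simulation has code loss by block, 5% of blocks in controls against 15% to 35% in SmoSz, guessing when lost, and 80% correct otherwise. It gives d = 0.19 to 0.53, and the t-test rejects in 14% to 71% of trials at 45 per group. With equal loss in both groups it rejects in about 5%.

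**Hypothesis 3, slope.** Assume only cognition affects breath CO (standardised slope −0.35) and accuracy correlates r with cognition within groups. The group-adjusted accuracy slope is then −0.35r:
- r = 0.3, 0.5, 0.7: −0.105, −0.175, −0.245.

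Add an index with reliability 0.6 to the model, so that its variance is 1/0.6 = 1.667. The accuracy slope becomes −0.35r × 0.667 / (1.667 − r²):
- r = 0.3: −0.105 × 0.423 = −0.044
- r = 0.5: −0.175 × 0.471 = −0.082
- r = 0.7: −0.245 × 0.567 = −0.139

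So 42% to 57% of the bias remains. It vanishes only for an error-free index of the very ability that drives accuracy.

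**Hypothesis 3, error rates.** Simulation at 45 per group: equal nicotine sensitivity, a 1 SD cognitive deficit in SmoSz, cue control driven by cognition alone (slope 0.5), accuracy loading 0.3 to 0.5 on cognition.
- Planned model: accuracy falsely significant in 28% to 67%; the 25% rule met in 11% to 47%, against about 1% at zero loading.
- Joint model: accuracy significant in 5% with an error-free index, 9% to 19% with reliability 0.6.

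**The case against.** The strongest reply is that the plan already holds an analysis that needs no letter code. The secondary test for Hypothesis 2 compares subjective state after each cigarette type, and participants also rate wanting, satisfaction and strength after each blind trial. Normal separation on ratings with poor accuracy would itself point to memory or labelling. This stands as a partial safeguard for Hypothesis 2. It does not reach Hypothesis 3, which uses accuracy.

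Second, 80 to 100 minutes is the worst case, at the fourth trial of a block; the shortest delay is 20 minutes and the references are refreshed before block 2. This stands.

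Third, a reader might infer that accuracy is in substance a cognitive score. The documents do not support that. They describe cognitive control deficits, not failure to hold a two-item code for an hour. Mental retardation and neurological illness are excluded, and patients must score at least 10 of 12 on the consent evaluation. A written reminder may exist in the discrimination questionnaire or the Study Manual, whose contents are not shown.

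Fourth, a reader might expect accuracy by trial position to settle the matter. With two binary trials per position per person, power to see a group gap widening across positions is only about 18% to 30% under assumed rising loss (5% to 35%, or 10% to 50%), and about 5% if loss is constant. A null result would falsely reassure.

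Fifth, the plan does not forbid a joint model. True, but it does not state one either, and the aim needs one.

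**Conclusion.** The point holds in limited form. The response task makes memory of the code a possible component of accuracy, and no stated model contains both accuracy and the cognitive control index, so the and/or aim has no planned analysis that separates its two parts.

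The direction, towards apparent nicotine insensitivity in SmoSz, is plausible. The size is unknown: every d, slope and error rate above rests on assumed lapse rates, correlations and reliability. They show that the effect could be of the order the trial is sized to detect, not that it is.

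Two stronger inferences fail. A positive Hypothesis 2 would not be invalid on this ground, since the ratings analysis can corroborate it. Nor would a joint model clear the confounding: the index comes from cognitive control tasks, is measured with error, and does not measure memory for labels. This is something the plan should address; it does not undermine the trial.

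**What to change.** 1. **Hypotheses 3 and 4.** Pre-specify one joint model of cue control on group, discrimination accuracy and the cognitive control index. Base the and/or conclusion on each predictor's contribution given the other. Keep the two single-predictor models as descriptive.
2. **Hypothesis 2.** Keep the primary accuracy test unchanged. Name the already planned group by cigarette type analysis of subjective state as the corroboration to be weighed before a group difference is attributed to nicotine insensitivity. Accuracy adjusted for the cognitive index may be reported as a sensitivity analysis only. It should not gate the conclusion, because cognition is linked to diagnosis and adjustment may remove a true diagnosis effect.

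The cost is analysis-plan wording, since all variables are already collected. The downsides should be stated in the plan: wider standard errors for both predictors in the joint model, and only partial removal of the confounding.

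### Hypothesis 3 enters accuracy from only eight A/B trials as if it were error-free, so a true majority share may well miss the 25% rule unless true accuracy varies widely between participants

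*Combined protocol and SAP*

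**What the plan says.** Study Procedures, item 1, Nicotine Discrimination Session: "Four discrimination trials follow, in which the participant is blind with regards to cigarette identity". After each trial "participants choose whether the sampled cigarette was of type A or B". Following lunch and one further reference trial with each cigarette, participants "complete another 4 discrimination trials as described above". That is eight scored answers per person, with chance at 50%.

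Sample Size and Data Analysis, item 2, Hypothesis 3: "Regression analysis tests the impact of discrimination accuracy on cue control while controlling for the group effect". For the accounting question, "we measure the reduction in the group effect when entering discrimination accuracy", "with a >25% reduction in β group defined as significant". A variance-explained version by ANCOVA follows. The cue-control outcome is taken from Hypothesis 1, which is tested by "comparing groups on breath CO after 8 hrs of ad libitum VLNCcig smoking". Hypothesis 4 "is tested in a manner analogous to Hypothesis 3".

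The Sample Size and Data Analysis section gives no reliability for the accuracy score, no correction for measurement error, and no interval or test for the reduction. The composite subjective-state score is a secondary analysis under Hypothesis 2 and is not named as a predictor under Hypothesis 3.

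**The concern.** A proportion out of eight carries a large binomial error. When such a score is a covariate, its within-group slope on the outcome is pulled toward zero, while the group gap in mean accuracy is not biased. The fall in the group coefficient is the product of the two, so it is understated. Adding participants does not remove this bias.

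At stake is Aim 3, which asks whether nicotine insensitivity can account for the group difference in cue control. With a fixed 25% cut-off and no interval, a result below the line could mean that there is no mediation or merely that the score is noisy, and the plan has no way to tell these apart. The protocol attends to measurement quality elsewhere: CO readings are repeated and averaged, and neutral Stroop trials are dropped to gain reliability. The Hypothesis 3 predictor gets no comparable treatment.

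**Working it through.** **1. The plan's own figure.** The plan states 45 per group for d = 0.6 at 80% power (written as beta = 0.8). Alpha is not stated; I take two-sided 0.05. A two-sample t-test needs 44.6 per group, so 45, with power 0.804. The figure is reproduced. It concerns the group comparison; the documents give no power or expected share for Hypothesis 3.

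**2. Reliability of eight trials.** Let m be mean accuracy and s the between-person SD of true accuracy within a group. Then

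λ = s² / [s² + (m(1 − m) − s²)/8].

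The documents give neither m nor s, so these are assumptions. At m = 0.75, m(1 − m) = 0.1875:

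- s = 0.10: 0.0100 / (0.0100 + 0.1775/8) = 0.31
- s = 0.15: 0.0225 / (0.0225 + 0.1650/8) = 0.52
- s = 0.20: 0.0400 / (0.0400 + 0.1475/8) = 0.68

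At s = 0.05, λ is 0.10. At m = 0.85 the values for s = 0.10, 0.15 and 0.20 are 0.41, 0.63 and 0.79.

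**3. What the 25% rule then requires.** With non-differential error, expected apparent share ≈ λ × true share. To show more than 25%, λ must exceed 0.25 divided by the true share:

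- true share 50%: 0.25/0.50 = 0.50
- 60%: 0.25/0.60 = 0.42
- 75%: 0.25/0.75 = 0.33
- 100%: 0.25/1.00 = 0.25

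**4. Simulation.** Settings: 45 per group, total group effect d = 0.6 on CO, beta-distributed true accuracy, Binomial(8, p) scores, control mean 0.75, true share 60%.

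| SD of true accuracy | λ | λ × 60% | Median apparent share* | Rule met* | Rule missed, all runs |
|---|---|---|---|---|---|
| 0.10 | 0.31 | 19% | 14% | 19% | 72% |
| 0.15 | 0.52 | 31% | 26% | 54% | 42% |
| 0.20 | 0.68 | 41% | 35% | 76% | 21% |
| Error-free score | 1 | 60% | n/a | 94-97% | 2-6% |

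*Among runs with a significant group difference in CO.

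The medians lie somewhat below λ × 60% for two reasons. Runs with a significant CO difference have a larger total effect in the denominator. The group with schizophrenia also has lower mean accuracy, which lowers the pooled reliability slightly.

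**5. Sensitivity.** Over all runs at control mean 0.75, true shares of 51% and 75% miss the rule in 77% and 62% (SD 0.10), 53% and 26% (SD 0.15), and 34% and 8% (SD 0.20). At control mean 0.85, a 60% share misses in 64% at SD 0.10 and 32% at SD 0.15.

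**6. Can the two blocks correct it?** Using the covariance of the two 4-trial scores as the true-score variance roughly removes the bias in the median, but the estimate is unstable. At λ = 0.31 and a true share of 60%, the central 90% of corrected shares ran from −0.86 to 2.72. With a true share of zero, the corrected share exceeded 25% in 7-23% of runs; in a separate simulation the uncorrected share did so in 1-2%.

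**The case against.** The strongest reply is that the size of the problem rests on a spread of accuracy that the documents do not give. A reader might infer that a true majority share would usually miss the 25% rule. That is not supported. At control mean 0.75 it holds for shares of 51-60% only when the SD of true accuracy is about 0.12 or less. At SD 0.15 a share just over half is near a coin toss, and 60-75% shares usually pass. At SD 0.20 majority shares usually pass.

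A reader might also infer that the plan favours cognitive control (Hypothesis 4) over nicotine insensitivity, because the cognitive tasks last about 30 minutes each. The documents do not support that either. They plan no contrast between the two hypotheses, and the overall aim allows both to hold. The expectancy AX-CPT focuses on one trial type and the Stroop is scored as a difference, which can itself be unreliable. No reliability is given for either mediator.

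Two further points are fair. The plan never says that a reduction below 25% counts against Hypothesis 3, and Hypothesis 3 also has a regression test of accuracy and a variance-explained measure. Both use the same noisy score, however, so both are weakened too. The two-block correction is imprecise and assumes that the blocks are parallel, although the second follows nicotine exposure, lunch and fresh reference trials. That argues against basing the decision on the correction, not against reporting it.

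What stands is that the score is noisy, it enters uncorrected, and the bias runs in one direction.

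**Conclusion.** The point holds in this form: the Hypothesis 3 reduction is biased toward no mediation by a factor of about the reliability of an eight-trial score, and the plan neither estimates nor allows for this. Over reliabilities of 0.31 to 0.68, the chance that a true 60% share meets the rule, given a significant group difference, is about 19% to 76%, where an error-free score would give 94-97%. Even at the favourable end, about one such trial in four would miss it.

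These figures assume independent trials, no response bias, error of the same kind in both groups, CO measured without error, and two-sided alpha of 0.05. Learning or carry-over between trials could move reliability either way. The direction of the bias is well founded; its size is unknown until the reliability is estimated. It is a worthwhile, inexpensive improvement to the analysis plan. It does not show that Hypothesis 3 will fail or that Hypothesis 4 is favoured.

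**What to change.** In Sample Size and Data Analysis, item 2:

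- Report the split-half reliability of discrimination accuracy from the two 4-trial blocks, and the reliability of the cognitive control index used for Hypothesis 4.
- Report the reduction in the group coefficient with a bootstrap interval, in place of reliance on the bare 25% cut-off.
- Add a reliability-corrected estimate (two-indicator latent variable or errors-in-variables) as a sensitivity analysis with its own interval, and do not apply the 25% rule to it.
- State that an uncorrected reduction below 25% is not evidence against Hypothesis 3.

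Cost: a few sentences of plan text and modest analysis work, with no extra trials, visits or participants. The downside is that at 90 completers the corrected estimate will be very imprecise if reliability is low, and it depends on the morning and afternoon blocks measuring the same thing. Both limits should be stated beside the result.
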